5.4 Check-In and Run-In Assessment Criteria

Upon passing screening and meeting inclusion and not meeting exclusion criteria, the subject will present to the clinic for admission.

For Part I and Part II, the following criteria must be met at Day -1 for the healthy volunteer to be checked into the clinic:

- 1. Females must have a negative urine pregnancy test.
- 2. Must not have a QTcF >450 msec for males and >470 msec for females.
- 3. Must have a negative result obtained from the urine drug screen (UDS) and the alcohol test (urine ethanol).
 - a. Healthy volunteers who have a positive result for alcohol will be asked to refrain from alcohol and return the next day for retest. This may only occur once.
- 4. Must have a negative polymerase chain reaction (PCR) test result for COVID-19.

Confidential Page 32 of 108

If any of these criteria are not met, the subject will not be enrolled into the study.

For Part III, subjects must meet the following criteria in order to be checked into the clinic on Day -6:

- 1. Females must have a negative urine pregnancy test.
- 2. Must have a negative PCR test result for COVID-19.

For Part III, subjects must meet the following criteria in order to complete run-in, and proceed into the study on Day -1:

- 1. Tolerating daily dose of SUBOXONE SL film between 8mg/2mg 24mg/6mg (inclusive).
- 2. COWS score of ≤ 12 .

If any of these criteria are not met, the subject will not be enrolled.

5.5 Deviation from Inclusion/Exclusion Criteria

This study is intended to be conducted as described in this protocol. Waivers from inclusion and exclusion criteria are not allowed because they have the potential to jeopardize subject safety, the scientific integrity of the study or regulatory acceptability of the data. Indivior does not grant waivers to the protocol-defined inclusion and exclusion criteria, and strict adherence to these criteria as outlined in the protocol is essential.

The Principal Investigator (PI), sub-Investigator or suitably qualified designee will be responsible for identifying, documenting and reporting all deviations, which are defined as isolated occurrences involving a procedure that did not follow the study protocol or study-specific procedure. In the event of a major deviation from the protocol due to an emergency, accident or mistake (e.g., eligibility or dosing errors), the PI, sub-Investigator or suitably qualified designee must contact the Indivior Medical Monitor at the earliest possible time by telephone. This will allow an early joint decision regarding the subject's continuation in the study. This decision will be documented by the Investigator and the Sponsor. Deviations will be reported as required to the Institutional Review Board (IRB) per their reporting process and criteria, and in the final study report.

Confidential Page 33 of 108

STUDY CONDUCT 6

Subject Enrolment 6.1

Indivior

Study participation begins once written informed consent is obtained; a subject identification (ID) number is then assigned. The subject ID will be used to identify the subject during the screening process and throughout study participation. A subject is considered enrolled once randomized in Part I or Part II, and in Part III, if Day -1 run-in assessment criteria are met.

The Investigator is responsible for maintaining a master list (i.e., a subject ID list) of all consented subjects. This document will be reviewed by Indivior or designated representative for accuracy and completeness. Ineligible subjects, as defined by the protocol-specific inclusion and exclusion criteria, should not receive IMP and should be documented as screen failures.

Screen Failure 6.2

A subject will be considered a screen failure if written informed consent is obtained, but the subject did not meet inclusion criteria or met one or more exclusion criteria. The study site will keep a Screening Log documenting subjects who have signed an informed consent. Screen failure reasons will be documented on the Screening Log as well as collected in the electronic case report form (eCRF).

Run-in Failure 6.3

In Part III only, a subject will be a run-in failure if written informed consent is obtained, the subject did meet inclusion criteria and did not meet exclusion criteria, however did not move past the run-in period of the study, and did not receive IMP (see Section 9 for the definition of "IMP"). Run-in failures will be documented on the Screening Log and the reason for run-in failure will be collected in the eCRF.

Subject Completion 6.4

For Parts I and II, a completed subject is one that completes the EOS visit. The end of the study is defined as the last subject's last visit.

For Part III, a completed subject is one who receives all scheduled doses of INDV-2000 and completes Day 14 safety assessments.

6.5 **Dose Escalation and Stopping Criteria**

The Data Review and Safety Committee (DRSC) will review blinded data from cohorts in Part I and Part II of the study and will determine if the dose can be escalated as planned, or alternatively, if any stopping criteria have been met. See Section 15.2

Confidential Page 34 of 108 Dose escalation will be dependent upon observed safety, tolerability and PK, but the increase from one cohort to the next will not exceed 2-fold in dose. In no case will the maximum daily drug exposure exceed that observed at the NOAEL in the most sensitive toxicology species.

The DRSC will also review individual subjects as needed to determine if the individual's participation should be stopped based on emerging safety and PK data.

6.5.1.1 Part I and II - Individual Stopping Criteria

If the following criteria are met at any point during Parts I or II, the affected individual's dosing will be paused to allow unblinded review of affected individuals by the DRSC before continuing dosing. A healthy volunteer will be discontinued if any of the criteria listed below are confirmed:

AEs:

• The healthy volunteer experiences an SAE that is not clearly unrelated to the IMP.

Laboratory Abnormalities:

The healthy volunteer has an abnormality of one or both of the following parameters, whose temporal relationship to the IMP makes causality plausible, confirmed on repeat testing:

- Serum ALT or AST >3 times the ULN
- Total serum bilirubin >2 times the ULN (>35% direct bilirubin).

Vital Signs:

The healthy volunteer fulfils one or both of the following vital sign criteria based on the mean of triplicate measures (≥ 1 minute apart), that will be completed once the first blood pressure reading is outside the accepted range:

- Systolic blood pressure (SBP) <85 or >170 mmHg and/or change from Baseline >30 mmHg sustained for at least 1 hr (measures repeated every 15 min)
- Diastolic blood pressure (DBP) <45 or >105 mmHg and/or change from Baseline >30 mmHg sustained for at least 1 hr (measures repeated every 15 min)

ECG Criteria:

The healthy volunteer fulfils the following ECG criteria based on the mean of triplicate measures (≥ 1 minute apart), that will be completed once the first ECG demonstrates a prolonged interval:

• QTcF ≥500 msec or uncorrected QT interval of >600 msec.

Plasma INDV-2000 Concentrations

Confidential Page 35 of 108

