6.5.1.2 Part I and II – Cohort Stopping Criteria

The study will be paused pending evaluation of all available data by the DRSC if any of the criteria listed below are fulfilled for an individual dosing cohort. The DRSC will conduct a review of unblinded data of the affected individuals to determine if any additional safety monitoring or changes to the protocol are required.

AEs:

- Three healthy volunteers experience a similar severe AE that is not clearly unrelated to the IMP, or
- Two healthy volunteers experience a similar SAE that is not clearly unrelated to the IMP.

Laboratory Abnormalities:

Two healthy volunteers with an abnormality of one or both of the following parameters, whose temporal relationship to the IMP makes causality plausible, confirmed on repeat testing:

- Serum ALT or AST >3 times the ULN.
- Total serum bilirubin >2 times the ULN (>35% direct bilirubin).

Vital Signs:

Two healthy volunteers fulfil one or both of the following vital sign criteria based on the mean of triplicate measures (≥1 minute apart), that will be completed once the first blood pressure reading is outside the accepted range:

- SBP <85 or >170 mmHg and/or change from Baseline >30 mmHg sustained for at least 1 hr (measures repeated every 15 min)
- DBP <45 or >105 mmHg and/or change from Baseline >30 mmHg sustained for at least 1 hr (measures repeated every 15 min)

ECG Criteria:

Two healthy volunteers fulfil the following ECG criteria based on the mean of triplicate measures (≥ 1 minute apart), that will be completed once the first ECG demonstrates a prolonged interval:

• QTcF ≥500 msec or uncorrected QT interval of >600 msec.

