9.1.1 Drug Manufacturer

9.1.2 Placebo

9.1.3 Blinding and Randomization

Part I and II of this study will be double-blinded to include the healthy volunteers, the Investigator and site staff. The clinical pharmacist and his/her designated team members responsible for IMP dispensation will be unblinded. The DRSC members will be blinded except for the Indivior PK scientist. The DRSC will review blinded clinical safety and laboratory data. Blinded PK data for dose escalation decisions may be presented, and if PK data cannot be presented in a blinded manner, the unblinded PK scientist will make blinded statements regarding those data to aid in dose escalation decisions. The Sponsor team may unblind after the dose escalation decision per cohort has been made (Section 15.2).

Confidential Page 48 of 108

The randomization schedule and disclosure envelopes will be generated by an unblinded statistician. The unblinded statistician will not be involved in any decisions relating to the study prior to unblinding. Prior to database lock and unblinding, all randomization materials, including the final signed and dated randomization schedule, will be held by the Indivior unblinded statistician.

A copy of the randomization schedule will also be made available to the unblinded team at the clinical site, as well as the laboratory performing the bioanalysis to allow selective analysis of PK samples to measure drug concentrations.

Interim PK parameter calculations will be performed using bioanalytical data with dummy subject numbers and initials in order to maintain the study blind. Interim PK analyses will be performed using nominal time points.

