10.1.3 Assessment of Causality

The Investigator or a medically qualified sub-Investigator, trained on this study protocol and listed on the delegation of authority log is responsible for determining the AE relationship to the study drug.

The following categories will be used to define the relationship of an AE to the administration of the study drug:

• Not Related: Data are available to identify a clear alternative cause for the AE other than the study drug.

Confidential Page 57 of 108

INDV-2000 Indivior Clinical Study Protocol: INDV-2000-102 09 May 2023

Related:

The cause of the AE is related to the study drug and cannot be reasonably explained by other factors (e.g., the subject's clinical state, concomitant therapy and/or other interventions).

A "reasonable possibility" is meant to convey that there are facts/evidence or arguments to suggest a causal relationship, rather than a relationship cannot be ruled out. The Investigator will use clinical judgment to determine the relationship. Alternative causes, such as natural history of the underlying diseases, concomitant therapy, other risk factors and the temporal relationship of the event to the study drug will be considered and investigated. The Investigator will also consult the IB in the determination of his/her assessment. For each AE/SAE the Investigator must document in the medical notes that he/she has reviewed the AE/SAE and has provided an assessment of causality.

There may be situations when an SAE has occurred, and the Investigator has minimal information to include in the initial report to Indivior or designated representative. However, it is imperative that the Investigator always make an assessment of causality for every event prior to the initial transmission of the SAE data to Indivior or designated representative. The Investigator may change his/her opinion of causality in light of follow-up information and amend the SAE data collection tool accordingly. The causality assessment is one of the criteria used when determining regulatory reporting requirements.

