15.2 Data Review and Safety Committee

The DRSC will include the Investigator, Sponsor Medical Monitor and PK scientist. Other members will be added as necessary. The DRSC members will be blinded except for the PK scientist. The DRSC will review blinded clinical safety and laboratory data. Blinded PK data for dose escalation decisions may be presented, and if PK data cannot be presented in a blinded manner, the unblinded PK scientist will make blinded statements regarding that data to aid in dose escalation decisions. Individual participant data may also be reviewed as needed (See Section 6.5). Based on the data presented, the DRSC may choose to unblind the data to the Sponsor only prior to making a dose escalation decision. Every effort will be maintained to keep the Investigator blinded. The proposed dose escalation scheme for Part I and Part II is described in the study design section; however, a more conservative dose escalation may be explored based on PK, safety and/or clinical observations. Dose escalation factors will be dependent upon observed safety, tolerability and PK.

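### Parts I and II: stopping-rule reviews send unblinded data to a DRSC that includes the Investigator and is elsewhere required to stay blinded, with no mechanism to keep the Investigator out

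*Protocol*

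**What the plan says.** **Stopping-rule reviews are unblinded.** Under Protocol Section 6.5.1.1, an affected volunteer's dosing is "paused to allow unblinded review of affected individuals by the DRSC before continuing dosing". Under Section 6.5.1.2, once a cohort criterion is met, "The DRSC will conduct a review of unblinded data of the affected individuals". Neither section names a subset of members, a closed session or a recusal.

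**The committee includes the Investigator and is blinded.** Section 15.2: "The DRSC will include the Investigator, Sponsor Medical Monitor and PK scientist", and "The DRSC members will be blinded except for the PK scientist". Section 9.1.3 agrees: "The DRSC members will be blinded except for the Indivior PK scientist". It also states: "Part I and II of this study will be double-blinded to include the healthy volunteers, the Investigator and site staff".

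**Other sections describe the committee's review as blinded.** Section 6.5 says the DRSC "will review blinded data from cohorts in Part I and Part II of the study" to decide on escalation and on whether stopping criteria are met. Section 14.11 likewise describes a blinded review after each cohort that uses the Section 6.5 rules.

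**The partial safeguard.** Section 15.2 lets the DRSC unblind data to the sponsor alone ahead of an escalation decision. It then states an intention to keep the Investigator blinded, without a procedure.

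**The rater.** Under Section 10.1.3 the Investigator, or a qualified sub-Investigator, "is responsible for determining the AE relationship to the study drug". Section 10.1 makes the Investigator ultimately responsible for AE assessment. Severity and relatedness of TEAEs are part of the primary endpoint (Sections 3.1 and 14.7.1).

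**The concern.** The two sets of instructions cannot both be followed. A site that applies Sections 6.5.1.1 and 6.5.1.2 literally puts treatment codes before a committee on which the Investigator sits. A site that applies Sections 9.1.3 and 15.2 literally cannot hold the review that Section 6.5 prescribes.

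At stake is blinded assessment of the primary safety endpoint. Unblinding would happen when the most consequential events occur. It could also feed back into the rules: AE triggers depend on whether a link to the IMP has been ruled out, and laboratory triggers on whether causality is plausible. An Investigator who knows the allocation of a first case may judge the next similar case differently, and that judgement can decide whether a cohort criterion is met.

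**Working it through.** The sample size is not power-based (Section 14.2), so the plan gives no figure to reproduce. The check is a comparison of sections, with simple counting for scale.

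**Step 1. Do the sections conflict?**

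| Question | Sections 6.5.1.1, 6.5.1.2 | Sections 6.5, 9.1.3, 14.11, 15.2 |
|---|---|---|
| Is DRSC review against stopping criteria blinded? | No, for affected individuals | Yes |
| Which members see unblinded data? | The DRSC, no subset named | PK scientist only |
| Is the Investigator a member? | Not addressed | Yes (15.2) |
| Is there a sponsor-only route? | None | Yes, but for dose escalation |

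One could read the stopping-rule sections as a specific exception to a general rule of blinding. That reading removes the contradiction only by admitting the Investigator to unblinded data, which Section 15.2 means to avoid.

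**Step 2. Which ratings are exposed?**
- *Initial SAE causality:* largely protected. Section 10.1.3 requires an assessment before the first report, and Section 11.2.1 requires that report within 24 hours.
- *Later revision of causality:* exposed. Section 10.1.3 permits it when follow-up information arrives.
- *Non-serious AEs not yet rated:* exposed. No timing rule applies.
- *Later similar events in other subjects:* exposed, through what was learned from the first case.
- *Intensity of numerically graded abnormalities:* largely protected. Appendix 6 grades blood pressure, ALT/AST and bilirubin mainly by cut-offs.
- *Intensity of other AEs:* exposed where it rests on the mild/moderate/severe definitions in Section 10.1.2.

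**Step 3. What is learned about subjects?** Inputs: 12 per cohort, 9 active and 3 placebo (Section 5.1). Over four cohorts that is 4 × 12 = 48 subjects, as stated, with 36 active and 12 placebo. Before unblinding, P(active) = 9/12 = 75%. For an affected subject it becomes 0% or 100%. If *a* of *k* revealed subjects are active, each remaining subject has P(active) = (9 − a)/(12 − k):

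| Revealed | Result for each remaining subject |
|---|---|
| 1 active | 8/11 = 72.7% |
| 1 placebo | 9/11 = 81.8% |
| 2 active | 7/10 = 70.0% |
| 1 of each | 8/10 = 80.0% |
| 2 placebo | 9/10 = 90.0% |
| 3 active | 6/9 = 66.7% |
| 3 placebo | 9/9 = 100% |

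The main effect is on the affected subjects. Leakage about the others is usually small.

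**Step 4. What does one changed rating do?** In an active cohort, related-TEAE incidence moves by 1/9 = 11 percentage points. For placebo it moves by 1/6 = 17 points if pooled within a Part, or 1/12 = 8 points if pooled over all four cohorts.

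**The case against.** A reader might infer that Section 6.5 necessarily unblinds the Investigator and that every rating of a triggering event is compromised. The documents do not support that. Section 6.5 refers to Section 15.2, which refers back to Section 6.5 for individual data and states the intention to keep the Investigator blinded. Read together, they leave unblinding possible and the mechanism unstated. For AE and laboratory triggers some causality judgement must already have been made before the review, and for SAEs it must precede the first report.

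A reader might also quote the share of a cohort unblinded by the cohort rule: 2/12 = 17% to 3/12 = 25%. That depends on a trigger whose probability is not given. It also largely repeats subjects already reviewed unblinded under the individual rule: apart from three similar severe AEs, each cohort criterion has an individual counterpart.

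Three further points have some force:
- Section 9.1.3 already lets the Investigator open disclosure envelopes for medical safety or when a scheduled safety review warrants it, so individual unblinding is foreseen.
- A sub-Investigator who is not on the DRSC may rate causality.
- The primary endpoint is summarised descriptively, so no type I error or power is at stake.

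These points limit the harm but do not remove the conflict. The intention in Section 15.2 follows a sentence confined to dose escalation, and neither stopping-rule section invokes it. The use of a sub-Investigator is optional. The envelopes are for particular need, whereas the review in Section 6.5 is prescribed whenever a criterion is met.

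**Conclusion.** The point stands as an internal contradiction in Parts I and II that may expose a rater of the primary endpoint to the allocation of affected subjects. It does not apply to Part III, which is open-label, and the SAP, which covers Part III only, does not address it.

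The risk is assessment bias in a descriptive safety summary. It is confined to the exposed ratings in Step 2 and arises only if a stopping criterion is met. The counts in Step 3 assume that the Investigator knows the 9:3 ratio, which the protocol states. The shifts in Step 4 assume full cohorts and show scale; they do not predict that ratings will change. Confidence is high in the contradiction and lower in the amount of bias. The sponsor should correct it because the remedy is cheap and carries out what Section 15.2 already intends.

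A related conflict must also be reconciled. Section 6.5.1.1 foresees an unblinded review followed by possible continuation of dosing, while Section 9.1.3 has subjects unblinded because of an AE leave the study.

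**What to change.** 1. Reword Sections 6.5.1.1 and 6.5.1.2 so that unblinded data go only to named members other than the Investigator: the already unblinded PK scientist and, if needed, a sponsor physician. The Investigator supplies blinded clinical facts and receives only the recommendation.
2. Require causality and severity of the triggering event to be recorded before any unblinding, and flag later changes in the data.
3. Align Sections 6.5, 9.1.3, 14.11 and 15.2 with this route. Leave emergency unblinding unchanged.
4. Reconcile Sections 6.5.1.1 and 9.1.3 on what follows for a subject unblinded because of an AE.
5. If Parts I and II have already run, state in the CSR whether such a review took place, who saw the allocation, and whether ratings had been recorded beforehand.

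**Cost.** Items 1 to 4 are mainly protocol wording, with a small addition to data recording. The Investigator does not see allocation during the review. If the sponsor physician is the Medical Monitor, a blinded DRSC member who takes part in dose escalation is unblinded for the affected subjects. Naming a different sponsor physician avoids this, at the cost of involving one more person.

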6.5.1.2 Part I and II – Cohort Stopping Criteria

The study will be paused pending evaluation of all available data by the DRSC if any of the criteria listed below are fulfilled for an individual dosing cohort. The DRSC will conduct a review of unblinded data of the affected individuals to determine if any additional safety monitoring or changes to the protocol are required.

AEs:

- Three healthy volunteers experience a similar severe AE that is not clearly unrelated to the IMP, or
- Two healthy volunteers experience a similar SAE that is not clearly unrelated to the IMP.

Laboratory Abnormalities:

Two healthy volunteers with an abnormality of one or both of the following parameters, whose temporal relationship to the IMP makes causality plausible, confirmed on repeat testing:

- Serum ALT or AST >3 times the ULN.
- Total serum bilirubin >2 times the ULN (>35% direct bilirubin).

Vital Signs:

Two healthy volunteers fulfil one or both of the following vital sign criteria based on the mean of triplicate measures (≥1 minute apart), that will be completed once the first blood pressure reading is outside the accepted range:

- SBP <85 or >170 mmHg and/or change from Baseline >30 mmHg sustained for at least 1 hr (measures repeated every 15 min)
- DBP <45 or >105 mmHg and/or change from Baseline >30 mmHg sustained for at least 1 hr (measures repeated every 15 min)

ECG Criteria:

Two healthy volunteers fulfil the following ECG criteria based on the mean of triplicate measures (≥ 1 minute apart), that will be completed once the first ECG demonstrates a prolonged interval:

• QTcF ≥500 msec or uncorrected QT interval of >600 msec.

